## **F. Provisions for Participant Privacy and Data Confidentiality**

As a requirement from our funder, de-identified data will be provided to the Coordination and Data Collection Center (CDCC). This is referred to as a data library in the consent and assent. Data will not be identifiable and will be shared using secure processes and procedures as designated by the CDCC.

### **1. Privacy**

**De-identified protected health information participants.** Potential participants will be identified by community partners (e.g., county public health agencies or a local health care provider) and the research team will not have access to their information, other than the data described in the methods, materials and assessment section. Participants will be tested in an environment that meets the patient privacy standards of the care provider (e.g., behind a partition, or in their vehicle at a drive-up event).

**Individual level survey data.** During the intervention, it will be up to participants to disclose vulnerable information about their previous experiences. Though testing will occur in public spaces, as is common in current pop-up testing across Oregon, efforts will be made to ensure that participants will be recruited, consented or assented, and tested in a private environment (e.g., behind a partition, facing away from others, in their vehicle, etc). Participants will only disclose contact information they feel comfortable disclosing, which may include email, phone number, or physical address.

**Anonymous participant interview.** Participants will not be asked to provide any identifiable information during the anonymous participant interview. In addition, efforts will be made to ensure participant confidentiality. For example, the interview will be conducted out of earshot from others. This aspect of the study is now complete.

**Promotores activities.** While promotores must participate in the knowledge assessment post training to determine adequate skill and knowledge to perform their role and must complete fidelity checklists to ensure program integrity, they will be able to elect to respond to questions asking for information about their personal characteristics or experiences related to the training.

**Community Based Organization general outreach activities.** CBOs will never be identified by name in any external scientific reports, however CBO contracts are federally funded and thus publicly available so there is potential that CBOs could be identified.

### **2. Data Disposition**

**De-identified protected health information participants.** Participant research data and samples will be collected without individual identifiers. Data will be maintained by the research study team. Barcode identifiers will be used to link survey data to biospecimens. The research team may be

briefly in possession of identifiable information while transporting diagnostic samples and only team members listed on the protocol will be involved in the transportation of diagnostic samples.

**Individual level survey data** Identifiable participant information will be collected in Qualtrics or RedCap during each survey. Following data collection, identifiable data will be removed, and a unique identifier assigned for all analyses. Protected health information from the sample collection intake form will be collected and stored by the University's CLIA laboratory. Only participants who provide consent or assent to share identifiable data with the study team will have their identifiable data shared with the study team. Disposition of email, phone number, or physical address will include keeping these data separate from the client survey data for analysis.

**Anonymous participant interview.** This component does not include the collection of individual identifiers. Audio recordings of participant interviews will be maintained on the secure server at the Prevention Science Institute (see confidentiality). Immediately following transcription, audio files will be destroyed.

**Promotores activities.** Identifiable participant information will be collected in Qualtrics or RedCap during each survey. Following data collection, identifiable data will be removed, and a unique identifier assigned for all analyses.

**Community Based Organization general outreach activities.** CBOs will never be identified by name in any external scientific reports, however CBO contracts are federally funded and thus publicly available so there is potential that CBOs could be identified.

### 3. Confidentiality

**All data points.** All de-identified research survey data will be stored at the Prevention Science Institute using standard security techniques (password protected file folders on the University's Prevention Science Institute secure server). Data from Qualtrics or RedCap will only be accessed using secure wifi. GC3F will store the viral RNA data on Talapas. Any sharing of de-identified viral RNA or survey data will occur on shared drive (such as One Drive) that is password protected.

Storage of data will be stored electronically on a private server and will be directly uploaded only while using secure wifi. If the data must be transferred, they will be transferred using a secure client server. Study researchers and the students they supervise may be granted access to the de-identified data after signing a data use agreement, in order to complete analyses. Records will be kept for up to 3 years after the study has been completed.

In addition to our study's database and data storing procedures within the UO, data collected for the RADx-UP project that will be shared with the RADx consortium will be uploaded through a secure client server and maintained by staff at the Duke Clinical Research Institute (DCRI). Identifiable data will be shared with DCRI when permission is given in the informed consent form or assent form. Participants are given the option to share identifiable information with the DCRI on the informed consent form or assent form. Agreeing to share identifiable data with the DCRI is not a requirement for participants to be enrolled in the study. The DCRI manages data from all studies participating in the RADx Program. The DCRI maintains data in two separate databases, one that contains identifiable information and one contains de-identified information.

**Individual level survey data and promotores data.** The only individuals with access to identifiable participant information on Teleform, Qualtrics or RedCap will be those who have the appropriate human subjects training who need access to the data to complete their assigned role on the research team. The code and key with participant contact information will be retained in a locked file on the Prevention Science Institute (at University of Oregon) server with permissions granted to only to the study project coordinator and data manager.

Research funded by NIH automatically has a Certificate of Confidentiality associated with it. This is added protection against forced disclosure of research information in circumstances of subpoena.

## G. Potential Research Risks or Discomforts to Participants

**De-identified protected health information participants.** Potential risks and discomforts involved in participation include (1) possible violation of confidentiality. These risks are unlikely. All records obtained from the CLIA laboratory will be kept strictly confidential. Identification numbers will identify participants' data, not their names. Project staff will receive training on confidentiality, including data collection, data management, and reporting procedures.

**Individual level survey data.** Information risks, psychological risks, and social risks may occur as the result of participating in this study. Information risks include loss of privacy and/or breach of confidentiality. Since data will be collected using only private wifi (except when participants are not connected to secure wifi if they use their own device) and will be stored on a secure server, it is unlikely that loss of privacy will occur.

Psychological risks may occur such as guilt or loss of self-esteem while receiving the health intervention. It is likely that both the treatment as usual and the treatment conditions will improve sense of responsibility to engage in health behaviors without inducing guilt and improve self-esteem but not everyone receives treatment uniformly. Participants will be encouraged to seek services if they are in need of additional support.

Social risks may occur as a result of receiving services in public. Specifically, participants might feel uncomfortable engaging in the intervention if they do not have a private space to participate. This risk may be diminished by the fact that half of the participants at the intervention site will be offered the intervention, regardless of their participation in the research survey.

All risks will be communicated in the informed consent or assent process. Our consenting and assenting process informs participants that the information that they provide will be shared with NIH and the RADx program who will collaborate to combine data that are collected in a standardized way across the group of studies. In addition, participants are reminded that all data will be de-identified prior to sharing with anyone outside of our study or outside of the RADx-UP program. Participants have the option to agree to let the DCRI have access to identifiable information (i.e. name, address, contact information, and date of birth) by providing their initials on the informed consent or assent form.

The protocol involves intervention. The intervention includes a promotores or community navigator intervention that aims to increase testing utilization and health behaviors. This will involve outreach by promotores present at testing sites. Promotores will provide health information which includes information from the Centers for Disease Control that has been vetted by county public health professional. This research does not pose any additional risk over the services provided as usual since some communities provide similar interventions.

The funding agency required a Data Safety Monitoring Plan for this research at the time of funding proposal. A copy of the DSMP submitted to the funder is attached.

There is no established Data and Safety Monitoring Board/Committee (DSMB/C) as noted in the DSMP.

**Anonymous participant interview.** There are no physical risks for the individuals who choose to complete this interview, however, some participants may experience discomfort when asked behavior related questions. Participants who feel uncomfortable during any part of the interview have the option to skip any question. This aspect of the study has been completed.

**Promotores data.** Information risks and psychological risks may occur as the result of participating in this study. Information risks include loss of privacy and/or breach of confidentiality. Since data will be collected using only private wifi (except when participants are not connected to secure wifi if they use their own device) and will be stored on a secure server, it is unlikely that loss of privacy will occur. All risks will be communicated in the informed consent and assent process.

## **H. Potential Benefits of the Research**

The overall risk involved in the project is relatively minor, given the goals of the research. Participants would face similar levels of risk sharing their information with a clinic or other outdoor testing event in order to be tested for SARS-CoV-2 infection. Participants will benefit by receiving a free SARS-CoV-2 diagnostic test and educational information that could improve their health behaviors and reduce transmission of SARS-CoV-2 in their communities and around Oregon. Thus, others in the community would benefit from general participation if participants are identified as positive who previously did not know they were infectious, and if participants actively alter their health behaviors, whether infectious or not.

Individuals may receive benefits from participating in this research such as improvements in health behaviors and reduced likelihood of contracting and spreading COVID-19.

By participating in this research, the research team will be able to learn whether the promotores intervention would be generally useful over services as usual (a flyer about health behaviors).

## 2. Roles and Research Duties

Principal Investigators will assume responsibility for all scientific, administrative, financial, and operational aspects of the project.

Co-Investigators will:

- assist the PIs with administrative functioning of the overall project
- assist in facilitating the community-based participatory approach

- support the project's collaboration with key community stakeholders and interface with county collaboratives
- interface with funded RADx-UP Social, Ethical and Behavioral Implications program grantees (SEBI, NOT-OD-20-119) and other RADx-UP field sites to support novel research on social, ethical and behavioral implications of testing in underserved and/or vulnerable populations
- contribute to activities to support implementation of the proposed interventions
- oversee the implementation and improvement science methodology employed to address the study aims
- assist in administrative and communication aspects of the testing project between working groups and help coordinate with the CDCC
- coordinate testing activities across sites and supervise field research staff
- serve as expert technical consultant for molecular testing pipelines, including aiding in continuing improvement in testing throughput and in detection sensitivity for SARS-CoV-2 in biological samples
- assume responsibility for ensuring that the processes of sample acquisition, testing, and reporting are CLIA and HIPAA compliant
- serve as data analytic support
- serve as a consultant on data processes and data modeling
- play a leadership role in the design, optimization, and implementation of data science tools and approaches.

Research Assistants will support the implementation of testing sites throughout Oregon and will provide implementation support to County collaborators. RAs will also collect individual and community level data on intervention effectiveness and assist with data analyses and dissemination activities.

### 3. Training and Oversight

Co-investigators and research assistants will perform research activities within the scope of their training.

Training for research assistants who collect data from participants will be provided by the project coordinator. Training will include how to sanitize devices used for data collection, relevant human subjects training, and standardized processes and procedures for data collection.

Promotores will provide services similar to what they would provide as usual for community-based organization. Given they are part of the research study, but will not be responsible for answering questions about the research or collecting informed consent or assent, and given the possible limited understanding of academic processes and procedures, we are proposing an alternative human subjects training plan for these individuals. Specifically, a researcher with human subjects training will provide human subjects training during the promotores training already being conducted by the research team. All promotores will be added to the research plan and will complete Individual Investigator Agreements (IIA)s if they are not affiliated with the UO. Alternative training procedure and training dates will be documented in the research records.

### 4. Translator

At least two people who are proficient in Spanish will review all written study materials before providing materials to participating county health departments and community-based organizations.

4.3 Statistical Design and Power

A power convention of .80 and for an alpha level of .05 was chosen for evaluating the multilevel model for the proposed site level outcomes (Aim 1) and for the individual level outcomes (Aim 2 and Aim 3). The minimally detectable effect size (MDE) was estimated using Monte Carlo simulation with 1000 replications in *Mplus* 8.5. An advantage of the Monte Carlo simulation approach is the ability to estimate parameter bias, standard errors, and coverage of confidence intervals.

Figure 4.3.1 Phase II Study Design and Expected Sample Sizes by Unit of Analysis

Aim 1 Analyses

Converting the Odds Ratio from the site level preliminary studies and the per capita outcomes Cohen's d ranged from .45 to .60, medium effects. The primary outcome for Aim 1 will be the number of Latinx tested specified as a generalized linear multilevel Poisson model for the count model and as a general linear model for the per capita proportional measures. For Aim 1 analyses, the unit of analysis is the number of total events nested within site. Across the continuing Phase I and the proposed Phase II testing events, there will be a total of 24 events per month for a total of 11 months (264 events).

As an illustration of total number tested, formally, the primary generalized linear model will be the following:

$$\text{Level 1: } E(\text{Test Count}) = \lambda \\ \text{Log}[\lambda] = \beta_0 + \beta_1(\text{Historical Week}) + r$$

$$\text{Level 2: } \beta_0 = \gamma_{00} + \gamma_1(\text{Location Contrast}) \dots \gamma_2(\text{Site Characteristics}) + u_0 \\ \beta_1 = \gamma_{10} + u_1$$

$$\text{Mixed Model: } \text{Log}[\lambda] = \gamma_{00} + \gamma_{01}(\text{Location Contrast}) + \gamma_{02}(\text{Site Characteristics}) + \gamma_{10}(\text{Historical Week}) + u_0 + u_1 + r$$

Where
the
expected
count of
Latinx
tested

represented as $\log \lambda$ is regressed on level 1 historical calendar week β_1 and the effect of the site-location outreach contrast γ_1 is estimated at level 2 as location type effect, controlling for socio-demographic census characteristics of each site γ_2 . Nested models will be compared and evaluated for over or under dispersion, zero-inflation, and normality for the linear mixed model estimating per capita Latinx tested.

Aim 1 Power. To illustrate power, MDE was estimated for proportion of Latinx tested per capita Latinx population with 1000 replications. One advantage of *Mplus* is the ability to specify events per month according to the design in which 10 census-located sites from Phase 1 will be conducting 20 events per month; and in the other study arm, 4 events per month will be conducted via community partner-located sites. Additionally, the group contrast for location type is simulated according to the clustering design with the appropriate allocation (mean = .42 and variance = .25). Residual variance of number of tested Latinx was specified at .7 for level 1 and .5 for level 2 in order to estimate an intra-class correlation (ICC) of .40, a conservative parameter reflecting the site level ICC from the preliminary analyses ranging from .24 to .37 for the related Latinx testing outcomes described in the preliminary studies section. Covariate parameters were entered with and effect size (ES) of .30 for historical week, and .19 for site characteristics at level 2 with .91 coverage. Models showed that the study is powered .81 to minimally detect an ES of .50, a medium effect.

Aim 2 and Aim 3 Analyses

Both Aim 2 and Aim 3 analyses will focus on the individual unit of analysis. Aim 2 will evaluate whether Phase II implementation fidelity of the *Promotores de Salud* health intervention will improve testing, reduce vaccination hesitancy, and increase vaccine acceptance and health literacy. Aim 3 will focus on the social determinants of pre-post change in the likelihood of vaccination, repeated tested for those unvaccinated, and reduced vaccine hesitancy. Both Aims will be specified as within-intervention group pre-post change. In general, we will estimate pre-post linear mixed models for vaccine hesitancy and generalized linear mixed models for increased testing counts and vaccine acceptance.

Using vaccination as an outcome, both Aims 2 and 3 are formally represented as a multilevel Bernoulli logistic model predicting the likelihood of vaccination:

$$\begin{aligned} \text{Level 1: } \text{Prob}(\text{Vaccine}=1) &= \Phi \\ \text{Log}[\Phi/(1-\Phi)] &= \beta_0 + \beta_1(\text{BL Vaccine Status}) + \beta_2(\text{Social Determinants}) + \beta_3(\text{Historical Week}) + r \end{aligned}$$

$$\begin{aligned} \text{Level 2: } \beta_0 &= \gamma_{00} + \gamma_1(\text{Fidelity of Implementation}) + \gamma_2(\text{Location Contrast}) \dots \gamma_n(\text{Site Charateristics}) + u_0 \\ \beta_1 &= \gamma_{10} + u_1 \\ \beta_2 &= \gamma_{20} + u_2 \\ \beta_3 &= \gamma_{30} + u_3 \end{aligned}$$

$$\text{Mixed Model: } \text{Log}[\Phi/(1-\Phi)] = \gamma_{00} + \gamma_{01}(\text{Fidelity}) + \gamma_{02}(\text{Location Contrast}) + \gamma_{03}(\text{Site Characteristic}) + \gamma_{10}(\text{BL Vaccine Status}) + \gamma_{20}(\text{Social Determinants}) + \gamma_{30}(\text{Historical Week}) + u_0 + u_1 + u_2 + u_3 + r$$

Where the probability of getting vaccinated Φ is regressed on level 1 baseline vaccine status β_1 , which then estimates the change in vaccine status from pre- to post-*Promotores*. Aim 2 fidelity of implementation is then estimated at level 2 as γ_1 controlling for location type and site level characteristics. Aim 3 social determinants are estimated at level when shown here as β_2 .

Aims 2 and 3 Power. For the multilevel model addressing aims 2 and 3, based on our preliminary Phase I data, we expect a total of 1650 survey participants over 11 months (200 tests per month via census-located events and 100 tests per month in partner-located events, for a total of 300 tests/month, with a 50% enrollment rate into the survey \times 11 months). For the one-month follow-up we anticipate a 50% retention rate. For a total of 825 pre-post participants. Power was estimated using a two-level Monte Carlo simulation, with the ability to model pattern missingness via both location approaches. To be conservative a retention rate was estimated at .50 for the established Phase I location approaches which will include a higher frequency of events, and a retention of .40 was estimated as the missing data pattern for Phase II partner-located; moreover, the proportion of missing data patterns were specified using the proportional design allocation and an ICC of .30 for individual testing outcomes. The proposed study is powered .81 to detect a MDE of .32 for fidelity of implementation at level 2, and is powered .83 to detect an MDE of .11 for social determinant variables at level 1 with .92 coverage.

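### The SAP text supplied contains no model or power statement for the randomised comparison of 18 Promotores sites with 18 services-as-usual sites

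*SAP*

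**What the plan says.** **Protocol.** Section B asks two between-arm questions. Question 1a is whether Promotores outreach yields more completed tests, and more sites working at capacity, than basic outreach. Question 1b is whether a brief individual Promotores contact changes health behaviour more than a pamphlet alone. Section C assigns 18 sites to each arm and names Latinx testing rates at site level as primary. Section D plans surveys in both arms, up to 1,800 in each. It ends with one analysis sentence: normal-theory analysis of covariance on pre-post scores, for site and individual outcomes.

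**SAP section 4.3, Aim 1.** The count of Latinx people tested is modelled by multilevel Poisson regression, and the per capita measure by a linear model. The group term is "the effect of the site-location outreach contrast", which "is estimated at level 2 as location type effect, controlling for socio-demographic census characteristics of each site". The power paragraph defines the groups: "10 census-located sites from Phase 1 will be conducting 20 events per month; and in the other study arm, 4 events per month" at partner-located sites. The result is "Models showed that the study is powered .81 to minimally detect an ES of .50, a medium effect".

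**SAP section 4.3, Aims 2 and 3.** "Both Aims will be specified as within-intervention group pre-post change". Power is given for fidelity ("The proposed study is powered .81 to detect a MDE of .32 for fidelity of implementation at level 2") and for social determinants (.83 at .11).

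**Phases.** The SAP describes its events as follows: "Across the continuing Phase I and the proposed Phase II testing events, there will be a total of 24 events per month". Its worked example for Aims 2 and 3 is vaccination. The protocol text supplied mentions neither phases nor vaccination outcomes.

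**The concern.** In a cluster-randomised trial, the main job of the SAP is to fix how the randomised arms will be compared on the primary outcome. Here the detailed models address other questions. The Aim 1 coefficient compares kinds of testing location. The Aims 2 and 3 coefficients relate outcome to fidelity and to social determinants among people in the intervention group.

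Two things are at stake. First, the arm term, the handling of site clustering and the choice of a count or rate model for the primary result stay open, and could be chosen with the data in hand. Second, the .81 at .50 is the only power figure for a testing outcome at site level, so it could be quoted as the power of the randomised trial. It was not computed for that comparison.

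**Working it through.** **1. What each model and power figure concerns**

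| Source | Terms | Promotores v usual services? | Stated power |
|---|---|---|---|
| SAP Aim 1 model | location contrast, site characteristics, historical week | absent | .81 at .50 (location) |
| SAP Aims 2 and 3 model | fidelity, location contrast, site characteristics, baseline vaccine status, social determinants, historical week | absent | .81 at .32 (fidelity); .83 at .11 (social determinants) |
| Protocol section D sentence | pre-post analysis of covariance, terms not listed | not named; clustering not named | none |

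The arm is in 0 of 2 displayed models and 0 of 3 power statements.

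**2. The SAP's own arithmetic**

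- Events: 24 × 11 = 264, as stated.
- Surveys: (200 + 100) × 0.50 × 11 = 1,650, and 1,650 × 0.50 = 825, as stated.
- ICC: .5 / (.5 + .7) = .417, stated as .40.
- Allocation variance: .42 × .58 = .244, stated as .25.

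**3. Can the .81 be reproduced?** No. The number of partner-located sites and the scale of the effect size are not given. With k partner sites (assumed 4, 7, 14 or 26), 220 events over 10 census-located sites and 44 over the k sites:

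SE² = (.5 + .7/22)/10 + (.5 + .7/(44/k))/k

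For k = 7, SE² = .0532 + .0873 = .1405, so SE = .375. Across the four values of k, power by normal approximation (two-sided .05 assumed, no covariates) is:

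- .21 to .39 if .50 is a raw coefficient;
- .24 to .45 if it is a difference in total-SD units;
- .70 to .96 if it is a coefficient standardised on the total SD.

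The stated .81 lies inside the last range. These are all calculations for the location contrast.

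**4. Could the location contrast be the randomised arm under another name?** An 18 v 18 allocation has mean 18/36 = .50, but the simulation uses .42. If .42 is a share of sites, 10 census-located sites imply 10/.42 = 23.8 sites in total, or 10/.58 = 17.2 if the coding is reversed. Neither is 36. The SAP also splits the groups by kind of location and by event frequency (20 v 4 a month), not by outreach received.

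**5. Could the Aims 2 and 3 data hold both arms?** The 1,650 comes from all 300 expected tests a month at both location types, and no part is set aside for usual services. Either every site in that count delivers Promotores, so that arm is constant and has no estimable coefficient, or the count mixes arms. The text does not say which.

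**The case against.** **Much is unseen.** A part of the SAP was removed, Figure 4.3.1 (the design figure) is not shown, the preliminary studies section that the SAP cites was not supplied, and some protocol pages are missing. The SAP also presents its equations and its Aim 1 power as illustrations, and both level 2 equations contain an ellipsis. This limits the point to the text supplied but does not answer it. Section 4.3 is the statistical design and power section, it gives models and power for all three aims, and the mixed models written out in full have no ellipsis and no arm term.

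**The protocol's analysis sentence may cover the comparison.** It could accommodate one. It does not specify an arm term, clustering by site or a count or rate model, although sites are the randomised units.

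**The SAP may belong to another phase.** If so, leaving out the 18 v 18 contrast is not an error in that SAP. This stands as a possibility. The two documents share Latinx testing as an outcome, the Promotores intervention and a one-month follow-up, so they do not decide it. In that case the text supplied would hold no detailed analysis plan for the randomised trial, and the gap would remain.

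**Stronger readings that a reader might infer:**

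- *The differing volumes prove that these are different studies.* The protocol's testing total covers participants at all testing sites, and its introduction describes both NIH-funded and state-funded events. The SAP's 300 tests a month appear only as the base for survey enrolment, and surveys run only at NIH-funded events. The protocol's survey number is a ceiling, while the SAP's is an expectation.
- *The SAP survey sample has no usual-services participants.* Step 5 leaves this open.
- *The location comparison is non-randomised.* The SAP calls the partner-located sites the other study arm, and the visible text does not say how location type was assigned.

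**Conclusion.** The point holds and must be fixed. In the text supplied, the randomised contrast is absent from both displayed models and all three power statements, and the protocol's generic sentence does not fill the gap. Confidence in that absence is high. The cause is less certain: it may be an omission from this trial's SAP or a SAP written for a different phase. The conclusion assumes that the unavailable pages do not specify the 18 v 18 analysis.

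A reader might go further and infer that the .81 is wrong or that the randomised trial is underpowered. The documents support neither. The .81 cannot be checked without the number of partner sites and the effect-size scale. For 18 v 18 sites, no events per site, ICC or effect scale is stated, so any power figure would rest on borrowed inputs. What can be said is that no power has been stated for the randomised comparison.

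**What to change.** 1. State which study, phase and sites the SAP covers, and where the 18 v 18 analysis is specified.
2. For the 36-site trial, make the primary analysis a model of Latinx tests as a rate (a count with a Latinx-population offset, or the per capita measure). Include randomised arm as a site-level term, site as the cluster, and the SAP's week and site covariates. Add an arm comparison for the full-capacity outcome in question 1a.
3. For question 1b, use a two-arm, baseline-adjusted, site-clustered model on the surveys planned in both arms. First reconcile how 1b is assigned. Protocol section C randomises sites, while section G says that half of those attending an intervention site would be offered the intervention.
4. If the SAP covers the randomised trial, label the location, fidelity and social-determinant analyses as secondary, and state how location type was assigned. If it covers a separate phase, leave its Aim 1 contrast as it is and supply a separate plan for the randomised trial.
5. State power for 18 v 18 sites with the effect-size scale, events per site and ICC defined. Do not cite .81 at .50 for the randomised contrast.

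**Cost.** If both arms are in the data, as protocol sections C and D plan, the cost is SAP text and a new power run. If every SAP site delivers Promotores, an arm term cannot be estimated there, and the cost is a separate analysis plan for the randomised trial.
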